5. METHODS

The study is an investigator-initiated, prospective cohort, single site study. The study has two parts: one for ICU patients and one for out-patient clinic patients. The study will take approximately 21 months to complete. Inclusion is expected to run from May the 1st, 2022 or as soon as possible thereafter and will continue until 10 patients have been included in out-patient part and 15 patients in the ICU part. The inclusion period is expected to be 21 months.

In the ICU study, the patient will have a Swan-Ganz catheter and an arterial catheter inserted as part of standard clinical practice and transthoracic echocardiography is likewise routinely performed. If the patient is eligible and after giving informed consent, the ReDS ICU system is applied for 48 hours continuously monitoring, whereafter it will be removed, and the patient's participation in the study is completed. During the inclusion in the study, the following data will be recorded:

- 1) Body position (Upper body elevation, left or right recumbent position)
- 2) ReDS ICU Lung Fluid parameter

- 3) ReDS ICU tilt parameter
- 4) Changes in patient body position

Before initiating the following interventions, the patient is required to have been hemodynamic stable for at least 1 hour, with a mean arterial pressure (MAP) around 65 mmHg and a maximum fluctuation of vasopressor-need of 25%. During the 48 monitoring, the following tests will be done:

- 1) Raised leg test – Both legs raised to 45° for 10 minutes.
- 2) Upper body elevation test - Starting from 30° the upper body is elevated to 45° then back to 30°, then 15° and back to 30°.
- 3) Left and right lateral recumbent position to 15° test – First left lateral recumbent position for 10 minutes then back to supine, then right lateral recumbent position for 10 minutes and then back to supine.
- 4) PEEP test – 5 cmH₂O increase PEEP for 10 minutes.

For all interventions, changes in HR, MAP, dPAP, mPAP, CO, SAT and ReDS ICU parameters (tilt and lung fluid) will be recorded 10 minutes prior, during and 10 minutes following completion of each test (1-4) . The completion of all interventions is estimated to take about 3 hours. The intervention will be paused if necessary.

In the out-patient part, if the patient is eligible and provides informed consent, the patient will have 4 measurements of lung fluid, which will be done as home-visits by a study designated healthcare worker. The first visit will be after inclusion and the following visits will be 14 (+/-5) days, 28 (+/-5) days and 42 (+/-5) days after the first visit.

The visits are expected to take no more than 1 hour each. During each visit the following data will be recorded:

- 1) Height (only recorded at first visit) and weight (recorded each visit)
- 2) NYHA functional class
- 3) Presence of peripheral oedema
- 4) Orthopnea
- 5) Rales by auscultation
- 6) CardioMEMS measures
- 7) ReDS v2.7 measures lung fluid parameter

Endpoints

Primary endpoints

ICU part:

- Correlation between ReDS ICU fluid parameters and Swan-Ganz measurements including right atrial pressure, pulmonary wedge pressure, mPAP and dPAP.

Out-patient part:

- Correlation between ReDS v2.7 fluid parameters and CardioMEMS measurements

Secondary endpoints

ICU part

- Changes in ReDS ICU fluid parameters following changes in Positive End Expiratory Pressure.
- Changes in ReDS ICU fluid parameters following raised leg test.
- Changes in ReDS ICU fluid parameters following changes in body position.
- Changes in ReDS ICU fluid parameters following changes administration of diuretics and inotropic/inodilators

Out-patient part

- Correlation between ReDS v2.7 fluid parameters and body weight
- Correlation between ReDS v2.7 fluid parameters and CardioMEMs measure
- Correlation between ReDS v2.7 fluid parameters and dyspnea symptom evaluated by NYHA class.

SAFETY

Safety assessments will consist of registration and recording of adverse events (AEs), adverse device effects (ADEs), Serious Adverse Events (SAEs) and Serious Adverse Device Effects (SADEs). AEs, ADEs, SAEs and SADEs will be recorded during ReDS Pro System v2.7 and ReDS ICU monitoring time.

The following adverse device events (ADE) can be expected from both devices: Localized rash and redness of the skin.

Regarding, SAEs: The population of interest is vulnerable, and hospitalizations, prolonged ICU stay (ICU part), changes to medical therapy and death are considered likely.

Specifically trained medical personnel will be present during the study visits and secure adequate assessment of the relevant safety parameters listed above, along with timely and accurate treatment of possible complications to study procedures. If it is medically necessary in the opinion of the investigator or if it is the wish of patients, the patient will be withdrawn from the study. At any time can the patient withdraw from the study. Patients who withdraw from the study will not be replaced by others.

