The Remote Dielectric Sensing (ReDS) System is a non-invasive device that includes two sensors and a bedside console, and it is designed for the measurement of lung fluid using extremely low power electromagnetic waves. Fluid readings are displayed in volume percentage units. The ReDS Pro System V2.7 system has CE approval (3900874CE01) and FDA clearance. The Bedside Console consists of an embedded computer with a touch-screen display. The device is managed by computer software, which analyzes the measured signals and displays the measurement results. The console includes an electronic module and a wireless communications module. The system is portable, available at the patient's bedside and is AC-powered from a standard wall electrical outlet. The Sensor Unit is applied and positioned on the patient thorax according to anatomical markers over the patient clothes. The ReDS readings are stored locally on the device without any patient identifiers.

The ReDS ICU configuration is intended to allow continuous monitoring in the ICU setting, and except from the following main modifications the configuration is identical to the CE-marked ReDS Pro System V2.7 device: the sensors are converted to low-profile adhesive patch-sensors that are attached using standard biocompatible tape to the patient's skin for 48 hours in ICU setting. The sensors are disposable and intended for single-patient use. Cables can be detached and reattached by connectivity ports along the cable to support sensors replacement. A small tiltmeter to track chest sensor's orientation was added to support recording of postures. Additionally, the system software has been updated to support continuous monitoring.

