6. STATISTICAL CONSIDERATIONS

At the Heart Center ICU, Rigshospitalet, 20-40 patients with HF is admitted monthly from this patient population, 5-10 will require Swan Ganz monitoring and will eligible for the present study.

Around 30 patients have a CardioMEMS sensor implanted and are followed at the out-patient HF clinic at Rigshospitalet.

For this pilot study, we estimate that 15 patients in the ICU part and 10 patients in the out-patient part will be sufficient to evaluate the feasibility of the ReDs systems.

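### Out-patient part: about one ReDS reading per home visit and no repeat, so reading error dilutes the visit-level primary correlation and cannot be estimated directly

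*Protocol*

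**What the plan says.** Section 5 (Methods) states that in the out-patient part "the patient will have 4 measurements of lung fluid, which will be done as home-visits by a study designated healthcare worker". The schedule is four visits, with the later three timed from the initial one: "The first visit will be after inclusion and the following visits will be 14 (+/-5) days, 28 (+/-5) days and 42 (+/-5) days". The list of data recorded at each visit has a single ReDS item, "ReDS v2.7 measures lung fluid parameter", next to the CardioMEMS measures. The out-patient primary endpoint is "Correlation between ReDS v2.7 fluid parameters and CardioMEMS measurements".

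The device description at the front of the protocol says how a spot reading is taken: "The Sensor Unit is applied and positioned on the patient thorax according to anatomical markers over the patient clothes". On time, section 5 says "The visits are expected to take no more than 1 hour each".

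On size, section 6 says "we estimate that 15 patients in the ICU part and 10 patients in the out-patient part will be sufficient to evaluate the feasibility". Section 5 adds: "Patients who withdraw from the study will not be replaced by others".

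The protocol describes no repeat reading, repositioning, averaging or repeatability check, and it gives no figure for ReDS reading error.

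**The concern.** The sensor is placed by hand over clothing, so some variation from one placement to the next is plausible. Random error in one of two correlated variables pulls their correlation toward zero by the square root of that variable's reliability. A single reading per visit neither averages the error down nor shows how large it is. Readings about two weeks apart do not help, because a difference between them mixes reading error with true change in lung fluid.

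This matters most for within-patient change. Section 4 (Purpose) hypothesizes that ReDS picks up congestion before symptoms worsen, which is a change within a patient. True variation over 42 days is likely to be smaller than variation between patients, so the same reading error takes a larger share of it. If the correlation comes out low, the pilot would have little with which to judge how far reading noise contributed. This is a matter of data collection, so no later analysis can supply the missing repeats.

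**Working it through.** **Count from the protocol.** 4 measurements / 4 visits = 1 per visit. 10 patients × 4 visits = 40 pairs at most, fewer if anyone withdraws.

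**Attenuation within patients.** Let λ be the reading-error variance divided by the true within-patient variance. The reliability of the mean of k same-visit readings is 1/(1 + λ/k) if their errors are independent, and the expected correlation is the true one times the square root of that. The true r of 0.6 and the range λ = 0.25 to 1.0 are assumptions.

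| λ | one reading | mean of two | mean of three |
|---|---|---|---|
| 0.25 | 0.6 × √(1/1.25) = 0.54 | 0.6 × √(1/1.125) = 0.57 | 0.6 × √(1/1.083) = 0.58 |
| 0.5 | 0.6 × √(1/1.5) = 0.49 | 0.6 × √(1/1.25) = 0.54 | 0.6 × √(1/1.167) = 0.56 |
| 1.0 | 0.6 × √(1/2) = 0.42 | 0.6 × √(1/1.5) = 0.49 | 0.6 × √(1/1.333) = 0.52 |

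**Dependence on the analysis.** Assume that the variance of a single reading splits into 0.6 between patients, 0.2 true visit-to-visit change and 0.2 error.
- All visits together: reliability (0.6 + 0.2)/1.0 = 0.80, so the correlation shrinks by √0.80 = 0.89.
- Within-patient change: 0.2/(0.2 + 0.2) = 0.50, factor 0.71. Two readings per visit give 0.2/(0.2 + 0.1) = 0.67, factor 0.82.
- Patient means over four visits: (0.6 + 0.2/4)/(0.6 + 0.2/4 + 0.2/4) = 0.65/0.70 = 0.93, factor 0.96.

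**What repeats would identify.** With one reading per visit, three different situations give the same observed correlation: 0.50 × √0.95, 0.69 × √0.50 and 0.80 × √0.371 are all about 0.49. With duplicates they separate, because the correlation between the two readings estimates the reliability itself: 0.95, 0.50 or 0.37. Without duplicates, agreement across visits gives a lower bound. In the split above it would be 0.6, against a true reliability of 0.80.

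**How well repeats would measure the error.** Three readings at 40 visits give 40 × (3 − 1) = 80 degrees of freedom for the within-visit SD. For normal errors of equal size, its relative standard error is about 1/√(2 × 80) = 8%. Two readings give 40 degrees of freedom and 1/√(2 × 40) = 11%.

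**Sampling error for comparison.** With 40 − 10 − 1 = 29 within-patient degrees of freedom, the standard error of Fisher's z is 1/√28 = 0.19. An observed r of 0.42 then has a 95% interval of 0.08 to 0.67. For patient means (n = 10), an observed r of 0.50 has an interval of −0.19 to 0.86.

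**The case against.** **The count is inferred.** The four measurements could mean four occasions, with the number of readings on each left open. Section 8 says the device is used as the manufacturer instructs, and those instructions are not at hand. This stands: one reading per visit is the natural count, not a certain one. But if the number is open, it still needs fixing. CardioMEMS is recorded at the same visit, and an open number would allow a reading to be repeated only because it looks out of line.

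**The size is assumed.** This also stands. If single-reading reliability is 0.9 or more, a true correlation of 0.70 falls only to 0.66; at 0.5 it falls to 0.49. The protocol does not say which is nearer.

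**The endpoint is not specified as within-patient.** Correct. A reader might infer that reading error passes in full into the primary result, but patient means would remove most of it.

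**A weak result would not be wholly uninterpretable.** A reader might infer that a low correlation could never be told apart from a noisy reading. That goes too far. Stable readings across visits would argue against heavy noise; only unstable ones would stay ambiguous. Nor would repeats settle everything, since CardioMEMS error and wide intervals remain.

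**The gain is a best case.** Readings minutes apart share operator, clothing and posture. Averaging does not remove shared error, and the within-visit SD would leave it out.

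**A mean of three is a different procedure from a spot reading.** Fair, if the device is used as a single reading. Reporting the first-reading correlation beside the mean answers it.

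**Conclusion.** This is a cheap improvement to the design, not an error or contradiction in the protocol. With about one reading per visit, random reading error attenuates the visit-level correlation, most of all for within-patient change, and the study has no direct estimate of that error. Under the stated assumptions, repeating readings would raise the expected within-patient correlation by 0.04 (0.54 to 0.58) to 0.10 (0.42 to 0.52) at best. That is smaller than the sampling error, so the firmer gain is the repeatability estimate, which even 10 patients can supply with fair precision.

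A reader might also infer a definite loss of power. The protocol does not support that: section 6 sizes the study for feasibility and sets no significance level, power or target correlation, and no repeatability figure is given from which to compute a loss.

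**What to change.** In section 5, out-patient part:

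- State a fixed number of ReDS v2.7 readings per home visit: at least two, for example three. Remove and reposition the sensor unit between readings, and record all of them.
- Use the mean of the readings in the out-patient correlations, and report the primary correlation from the first reading alone alongside it.
- Report the within-visit SD, noting that it excludes error shared within a visit (same operator, clothing and posture).

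The cost is a few more minutes in a visit expected to last up to 1 hour, and one or two more eCRF fields. It needs no extra patients, visits or staff.

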7. PARTICIPANTS

ICU part

Inclusion criteria:

- at least 18 years of age
- hospitalized in ICU setting at Rigshospitalet
- intubated
- unconscious or sedated (Glasgow Coma Score <8)
- monitored using Swan-Ganz and arterial catheterization.

Exclusion criteria:

- pacemaker or ICD

- congenital heart malformations or intra-thoracic mass that would affect the right lung anatomy (e.g. dextrocardia, lung carcinoma)
- wounds, burns, healing tissue, skin infection or recent skin graft or flap where the sensors should be attached to the skin
- habitus is out of range due to one or more of the following
 - height less than 155 cm or higher than 195 cm
 - estimated BMI of less than 22 or more than 36
 - standard active therapy has been stopped as the patient is inevitably dying.

Out-patient part

Inclusion criteria:

- 1) at least 18 years of age
- 2) history of Chronic heart failure > 3 months
- 3) CardioMEMS

Exclusion criteria:

- 1) pacemaker or ICD on the right side
- 2) congenital heart malformations or intra-thoracic mass that would affect the right lung anatomy (e.g. dextrocardia, lung carcinoma)
- 3) wounds, burns, healing tissue, skin infection or recent skin graft or flap where the sensors should be attached to the skin
- 4) habitus is out of range due to one or more of the following
 - a. Height less than 155 cm or higher than 195 cm
 - b. BMI of less than 22 or more than 38
 - i. For BMI 36 to 38, chest size ruler should be 39 or less
- 5) cancer or other severe non-cardiac disease with estimated life expectancy less than 1 year
- 6) planned hospitalization for ICD, pacemaker, lung or heart surgery including heart transplantation during the study period.

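### Do the repeated CardioMEMS secondary and the loosely worded body-weight secondary in the out-patient part call for a change to the endpoints?

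*Protocol*

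**What the plan says.** Section 5 of the Protocol, under Endpoints, gives the out-patient primary as "Correlation between ReDS v2.7 fluid parameters and CardioMEMS measurements". The secondary list for the same part then contains "Correlation between ReDS v2.7 fluid parameters and CardioMEMs measure", alongside "Correlation between ReDS v2.7 fluid parameters and body weight" and a third correlation with NYHA class. No pressure variable, time point or scale separates the CardioMEMS secondary from the primary.

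On data collection, Section 5 states that "the patient will have 4 measurements of lung fluid", at a first visit and about 14, 28 and 42 days later. Weight and the CardioMEMS reading are taken at each of those visits. Section 6 presents the study as a pilot in which "10 patients in the out-patient part will be sufficient to evaluate the feasibility", with no alpha, power or target correlation. At the end of Section 5: "Patients who withdraw from the study will not be replaced by others". Section 7 excludes out-patients with "BMI of less than 22 or more than 38" or with a height outside 155–195 cm.

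**The concern.** Two things catch the eye. First, one comparison cannot usefully be both primary and secondary. Either the second line is redundant, or a different secondary was intended and lost in drafting.

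Second, the out-patient hypothesis in Section 4 is about detecting congestion before symptoms appear, which is a change in a patient over time. The ICU secondaries are worded as changes; the weight line is not. Read literally, it also admits a correlation of first-visit values, of patient means, or of all visits pooled as if independent. Each of these would be driven mainly by how heavy patients are relative to one another. A device that follows weight change and one that does not could then give much the same answer, although the data to tell them apart are collected.

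**Working it through.** **The duplicate.** Set side by side, the primary and secondary CardioMEMS lines name the same device, comparator, population and statistic. They differ only in a singular against a plural and in one capital letter. Section 6 defines no significance level, testing order or multiplicity rule, so nothing is counted twice.

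**Possible spread in weight.** Inputs are the Section 7 limits; weight = BMI × height².
- Extremes: 22 × 1.55² = 52.9 kg and 38 × 1.95² = 144.5 kg. This is an eligibility envelope, not the spread expected in 10 patients. BMI 36–38 also carries a chest-size condition.
- At a single height of 1.70 m, BMI 22 to 36: 22 × 2.89 = 63.6 kg to 36 × 2.89 = 104.0 kg.

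**What a correlation of levels would show.** The Protocol gives no SD, ICC or correlation, so all that follow are assumptions. Let SDb and SDw be the between- and within-patient weight SDs, and rB and rW the between- and within-patient correlations of ReDS with weight.
- Within-patient share of weight variance = SDw² / (SDb² + SDw²).
- Level correlation = rB × √(ICC_ReDS × ICC_weight) + rW × √((1 − ICC_ReDS)(1 − ICC_weight)), where ICC_weight = SDb² / (SDb² + SDw²).

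With ICC_ReDS = 0.7 and rB from −0.3 to 0.3:

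| SDb / SDw (kg) | Within share | Level r, rW = 0 | Level r, rW = 0.8 | Gain at equal rB |
|---|---|---|---|---|
| 20 / 1 | 1/401 = 0.25% | −0.25 to 0.25 | −0.23 to 0.27 | 0.022 |
| 15 / 2 | 4/229 = 1.7% | −0.25 to 0.25 | −0.19 to 0.31 | 0.058 |
| 10 / 3 | 9/109 = 8.3% | −0.24 to 0.24 | −0.11 to 0.37 | 0.126 |
| 5 / 3 | 9/34 = 26.5% | −0.22 to 0.22 | 0.01 to 0.44 | 0.225 |

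Example, 10 / 3 with rB = 0.3 and rW = 0.8: 0.3 × √(0.7 × 0.917) + 0.8 × √(0.3 × 0.083) = 0.240 + 0.126 = 0.366.

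**Simulation, 10 patients × 4 visits.** This estimates the chance that a tracking device (rW = 0.8) gives a higher correlation than a non-tracking one (rW = 0) at equal rB. It covers the first three rows of the table and rB of −0.3, 0 and 0.3, with 20,000 data sets per setting; 0.50 is a coin toss.
- First visit: 0.51–0.61.
- Patient means: 0.50–0.54.
- Pooled visits: 0.52–0.66.
- Patient as factor: above 0.99.

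With weaker tracking (rW = 0.5, SDs 15 / 2, rB = 0), pooled visits give 0.55 and patient as factor 0.98.

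**Precision of the within-patient analysis.** Fisher z with SE = 1/√(df − 1) and df = patients × 3 − 1. For an observed r of 0.5:
- 10 complete patients, df = 29: 95% interval 0.18 to 0.73.
- 8 patients (two lost before a second visit and not replaced), df = 23: 0.13 to 0.75.

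**Does the Protocol choose the weak analysis?** No. The weight line names two variables and a correlation. Four paired readings per patient make the repeated-measures version available without any new data.

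**The case for a change.** The strongest case for a change is that an endpoint line should name the quantity of interest, and that a SAP should not have to guess which secondary was meant. Rewording costs two lines. The numbers show that, if a pooled or single-visit correlation were used, the weight result would be close to uninformative about tracking.

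The conditional part of this stands: under the assumed SDs, those analyses do perform poorly. The step from there to a fault in the Protocol does not.
- Nothing in Section 5 selects a pooled or single-visit analysis. Not every analysis of weight levels is affected either, because a correlation of levels with patient as a factor removes body size.
- The primary and the NYHA secondary have the same form over the same four visits. If silence on within-patient analysis were a defect of the weight line, it would be one of those lines too.
- No part of the Protocol gives the weight secondary the purpose of showing that ReDS follows weight change. The Section 4 hypotheses concern congestion and CardioMEMS.
- Part of the overlap in the table comes from letting rB differ between the two devices. At equal rB, tracking raises the level correlation by 0.022 to 0.225, so a level-based result is weak rather than empty.
- Recasting the CardioMEMS secondary as a within-patient association would not reliably cure the duplication: if the primary is analysed with patient as a factor, the two coincide again.

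**Conclusion.** No change to the plan is needed. The repeated CardioMEMS line is a clerical slip. With no alpha or multiplicity scheme in the Protocol, the comparison will be reported once as the primary, and striking the second mention would change no result. If another variable was intended, only the investigators can say so; the text gives no hint of one.

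The weight secondary is a gap that an analyst fills sensibly. With four paired readings per patient, treating patient as a factor is the natural choice, the wording permits it, and the SAP may already specify it. A first-visit, patient-mean or pooled correlation would be a poor substitute: 0.2–8% of weight variance within patients, and a 0.50–0.66 chance of ranking a tracking device above a non-tracking one. Those figures rest wholly on assumed SDs, ICCs and correlations, and they describe an analysis the Protocol does not prescribe. Even the better analysis would be imprecise in 10 patients (0.18 to 0.73 around an observed r of 0.5), which suits a secondary endpoint in a feasibility pilot.
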